10.3 Patient demographics and baseline characteristics

Demographic and other baseline characteristics will be summarized for the Full Analysis Set (FAS). Baseline characteristics include prior medication, past/current medical conditions and disease history.

Medical history will be coded using MedDRA and will be presented by MedDRA system organ class, preferred term and treatment group. Separate tables will be provided for past medical conditions and current medical conditions. Prior medications and significant non-drug therapies will be coded according to the WHO Drug Reference List, and summarized by ATC class and preferred term using frequency distributions.

10.4 Treatments (study drugs, concomitant therapies)

Duration (days) of drug exposure will be summarized using descriptive statistics separately for everolimus and exemestane.

Duration of drug exposure will be calculated as the difference between the last and first day of drug application +1. Dosage averages will be calculated including and excluding zero doses for periods of temporary interruption of treatment, regardless of whether this was due to safety/tolerability reasons or patients' non-compliance. Average daily dose levels will be summarized descriptively. Frequencies of the number of patients with any dose reduction (including temporary dose interruption) as well as the number of dose reductions by reason will be given. These analyses will be performed on the Safety Set.

Concomitant medications and significant non-drug therapies prior to and after the start of the study drug will be coded according to the WHO Drug Reference List, and summarized by ATC class and preferred term using frequency distributions.

10.5 Primary objective

The primary objective is to evaluate the safety and tolerability profile of everolimus in post-menopausal women with ER positive, HER2 negative locally advanced or metastatic breast cancer after documented recurrence or progression following a non-steroidal aromatase inhibitor therapy in emergent growth markets (EGM).

The assessment of safety and tolerability will be based mainly on the frequency of adverse events, including the laboratory values that qualify as adverse events. Other safety data (e.g. vital signs, and special tests) will be considered as appropriate. The analysis will be descriptive. For all safety/tolerability analyses, the safety set will be used.

Data collected by AE CRFs will be coded using the MedDRA dictionary. The incidence of treatment-emergent adverse events (new or worsening from baseline) will be summarized by MedDRA system organ class and preferred term using frequency distributions. Additionally, AE will be summarized by maximum severity (based on CTCAE grades), and for AE with suspected drug relation, serious AE (SAE), and AE leading to permanent discontinuation of study drug. All information pertaining to AE noted during the study will be listed by patient, detailing the verbatim term given by the investigator, MedDRA preferred term and system organ class, start/end dates, severity, seriousness, relationship to study drug and action taken.

[figure not shown]
The AE onset will also be shown relative (in number of days) to the date of initial dose. AE starting more than 30 days after discontinuation of study drug will not be considered as treatment-emergent and will not be included in AE summary tables but listed only.

Data from other tests (e.g., electrocardiogram or vital signs) will be summarized descriptively as appropriate. Notable values will be flagged, and any other information collected will be listed as appropriate.

10.6 Secondary objectives

10.6.1 Efficacy endpoints

Efficacy endpoints will be analyzed on the Full Analysis Set (primary analysis) and on the Per Protocol Set (supportive analysis).

Efficacy endpoints based on radiological assessments of tumor burden will be derived using local radiologist's/ investigator's assessment. If a patient has not had an event before exiting the study, his or her data will be censored at the date of last adequate tumor assessment.

10.6.1.1 Overall response rate

The Overall response rate (ORR) will be provided over the study period. The ORR is the proportion of patients with a best overall response of confirmed complete (CR) or partial (PR) response at those time points. The best overall response for each patient is determined from the sequence of investigator overall lesion responses according to RECIST 1.1. To be assigned a best overall response of CR at least two determinations of CR at least 4 weeks apart before progression are required. To be assigned a best overall response of PR at least two determinations of PR or better at least 4 weeks apart before progression (and not qualifying for a CR) are required.

The ORR (best overall response of CR or PR) as well as individual response categories (CR, PR, SD, PD or unknown) measured at approximately week 20 and week 50 will be summarized using frequency tables together with their associated two-sided exact 95% confidence intervals (Clopper-Pearson method).

10.6.1.2 Clinical benefit rate

The clinical benefit rate (CBR) will be provided over the study period. CBR rate is defined as the proportion of patients with best overall response of complete response (CR), partial response (PR) or stable disease (SD), with duration of 24 weeks or longer, according to RECIST 1.1. The best overall response for each patient is determined from the sequence of investigator overall lesion responses according to RECIST 1.1. To be assigned a best overall response of CR or PR, two determinations of CR at least 4 weeks apart before progression are required.

[figure not shown]
The duration of best overall response is assessed as such: the start date is the date of first documented response (CR or PR) and the end date is the date of event defined as first documented progression disease or death due to underlying cancer.

The CBR measured at approximately week 20 and week 50 will be summarized using frequency tables together with its associated two-sided exact 95% confidence intervals (Clopper-Pearson method).

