As of June 30th 2014, 198 patients have been enrolled into the study.

At this stage we deem appropriate to change the end of study “until everolimus is locally reimbursed or commercialized for this indication or until all patients have been discontinued from investigational treatment due to disease progression, unacceptable toxicity, death, consent withdrawal or any other reason”, in order to:

- Facilitate treatment continuation at the single patient level in all participating countries
- Continue data collection and further strengthen the final safety and efficacy data set

The statistical plan was revised accordingly to take into account prolonged study duration and to ensure data will be analyzed will be mature enough to derive conclusive results. with primary efficacy and safety/tolerability analysis now planned at 15 months of median follow up time, i.e. at approximately two times the median PFS observed in the BOLERO-2 study.

On the other hand, as the investigational drug will be commercially available in the majority of the participating countries by the end of 2014, recruitment will end in any case in all participating countries no later than on 31st of October 2014.

Moreover, as substantial updates were included in the [Investigator’s Brochure] (version 13) recently released, relevant sessions of the protocol have been amendment accordingly, although this does not imply major changes in study implementation and conduction.

[figure not shown]
Additional minor changes were included to amend negligible inconsistencies in the previous version,

Changes to the background session:

- Updated information about everolimus clinical efficacy and safety profile have been included.

Changes to study design:

- It is specified that enrollment will end in all participating countries by the time of registration/commercial availability of everolimus in the investigational indication and in any case no later than October 31st 2014.

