4.1 Description of study design

This is an international, multi-center, open-label, single arm, phase IIIb study designed to collect clinical safety, tolerability and efficacy data with the use of everolimus combined with exemestane in post-menopausal women with HR positive, HER2 negative locally advanced or metastatic breast cancer after documented recurrence or progression following a non-steroidal aromatase inhibitor therapy, with no prior treatment by mTOR inhibitors, in the EGM countries. Enrollment will end in all participating countries by the time of registration/commercial availability of everolimus for the investigational indication or in any case no later than October 31st 2014. It is anticipated that up to 400 patients will be enrolled from a set of EGM countries of Novartis Oncology by this date.

In each participating country, the study will start after approvals are being obtained from the respective local authority and IRB and will end when everolimus is locally reimbursed or commercialized for this indication or when all patients have been discontinued from investigational treatment due to disease progression, unacceptable toxicity, death, consent withdrawal or any other reason.

In those countries in which patients will be transitioned to locally reimbursed or commercialized drug supply, Novartis will have a local transition plan in order to ensure that all on-going patients will still have access to the study medication without any delay in their treatment.

Data derived from the study will be collected, according to ICH GCP and any international and local regulations, to evaluate the safety, tolerability and efficacy of the combination of everolimus (10 mg daily) and exemestane (25 mg daily) in eligible patients.

The study comprises two periods:

Screening phase

Written informed consent must be obtained before any study specific medical procedures are performed. The investigator or his/her authorized designee will assign a unique number to patients being considered for the study. Each patient is uniquely identified by a 9-digit patient identifier (consisting of a 4-digit center number and 5-digit patient number). Once assigned, the patient numbers for patients will not be reused.

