4.2 Definition of end of the study

In each participating country, the study will start after approvals are being obtained from the respective local authority and IRB and will end when everolimus is locally reimbursed or commercialized for this indication or when all patients have been discontinued from investigational treatment due to disease progression, unacceptable toxicity, death, consent withdrawal or any other reason.

In those countries in which patients will be transitioned to locally reimbursed or commercialized drug supplies, Novartis will have a local transition plan in order to ensure that all on-going patients will still have access to the study medication without any delay in their treatment.

Patients will be followed up for safety purposes for 30 days (\pm 2 days) after the last dose of study drug. At the end of the study, the progression status of all participating patients will be updated and recorded in the electronic case report form (eCRF).

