Number of Patients in Safety Set	n (%)	xx (xx.x)	xx (xx.x)	xx (xx.x)	xx (xx.x)	xx (xx.x)	xx (xx.x)

Asian: Indonesia, India, Vietnam, Turkey, South Korea, Thailand, Malaysia, Taiwan or Jordan.

Non-Asian: Australia, Morocco, South Africa or Tunisia.

Table 1.2 Population Sets by Country - All Patients

Country	Enrolled n (%)	Full Analysis Set n (%)	Per Protocol Set n (%)	Safety Set n (%)
TOTAL	XXX	XXX	XXX	XXX
Australia, n (%)	xx (xx.x)	xx (xx.x)	xx (xx.x)	xx (xx.x)
:	:	:	:	:
Vietnam, n (%)	xx (xx.x)	xx (xx.x)	xx (xx.x)	xx (xx.x)

Note to programmer: This table will include the following countries in alphabetical order: Indonesia, India, Vietnam, Turkey, South Korea, Thailand, Malaysia, Taiwan, Jordan, Australia, Morocco, South Africa or Tunisia.

Table 1.3 Patients Disposition Overall and in Asian Subgroup – All patients

Disposition Reason	Asian (N=xx)	Non-Asian (N=xx)	Total (N=xx)
Patients enrolled, n (%)	xx (xx.x)	xx (xx.x)	xx (xx.x)
Untreated	xx (xx.x)	xx (xx.x)	xx (xx.x)
Treated	xx (xx.x)	xx (xx.x)	xx (xx.x)
Patients treated, n (%)	xx (xx.x)	xx (xx.x)	xx (xx.x)
Treatment ongoing	xx (xx.x)	xx (xx.x)	xx (xx.x)
End of treatment	xx (xx.x)	xx (xx.x)	xx (xx.x)
Primary reason for end of treatment	xx (xx.x)	xx (xx.x)	xx (xx.x)
Unacceptable adverse events	xx (xx.x)	xx (xx.x)	xx (xx.x)
Abnormal laboratory value(s)	xx (xx.x)	xx (xx.x)	xx (xx.x)
Abnormal test procedure result(s)	xx (xx.x)	xx (xx.x)	xx (xx.x)
Intercurrent illness that prevent further administration of everolimus treatment	xx (xx.x)	xx (xx.x)	xx (xx.x)
Consent withdrawal	xx (xx.x)	xx (xx.x)	xx (xx.x)
Lost to follow-up	xx (xx.x)	xx (xx.x)	xx (xx.x)
Administrative problems	xx (xx.x)	xx (xx.x)	xx (xx.x)
Death	xx (xx.x)	xx (xx.x)	xx (xx.x)
Disease progression	xx (xx.x)	xx (xx.x)	xx (xx.x)
Treatment duration completed within the scope of Expanded Access. Program (EAP) (till 31 DEC 2014)	xx (xx.x)	xx (xx.x)	xx (xx.x)
Patient is switched to commercial drug	xx (xx.x)	xx (xx.x)	xx (xx.x)
General or specific changes in the patient's condition which render the patient unacceptable for further everolimus treatment at the discretion of the investigator	xx (xx.x)	xx (xx.x)	xx (xx.x)
Need for any other types of anticancer therapy, except for palliative radiotherapy for bone lesions	xx (xx.x)	xx (xx.x)	xx (xx.x)
Everolimus dose interruption of > 4weeks	xx (xx.x)	xx (xx.x)	xx (xx.x)
Length of follow-up from screening to end of study (weeks) ^a			
n	xx	xx	xx
Mean (SD)	xx.x (xx.x)	xx.x (xx.x)	xx.x (xx.x)

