^a Best overall response rate: The best response recorded from baseline assessment until progression. CR: at least two consecutive determinations of CR at least 4 weeks or one determination of CR where confirmation not required prior to PD. PR: at least two consecutive determinations of PR (or better) at least 4 weeks or one determination of PR where confirmation not required prior to PD and not classified as PR. SD: one determination of SD (any duration) prior to PD and not classified as CR or PR. PD: one determination of PD (any duration) and not classified as CR, PR or SD. Unknown: not classified as CR, PR, SD or PD.

^b Overall response rate: Patients with best overall response rate of CR or PR.

^c Clinical benefit rate: Patients with best overall response rate of CR (any duration), PR (any duration) and SD with duration of 24 weeks or longer.

N: The total number of patients in the treatment group. It is the denominator for percentage (%) calculation.

n: Number of patients who are at the corresponding category.

CI: Confidence interval. The 95% CI for the frequency distribution of each variable were computed using the Clopper-Pearson method.

Programmer note: This table is not created by Kaplan Meier method. It is a summary of descriptive statistics based on week 20 and week 50 CRF data. n is the number of patients with non-missing data.

Table 8.1.2 Overall Response Rate *Overall and in Asian Subgroup - Per Protocol Set*

This table will be created using the same layout as Table 8.1.1.

Table 8.1.3 Time to Overall Response Overall and in Asian Subgroup – Full Analysis Set

	Asian (N=xx)		Non-Asian (N=xx)		Total (N=xxx)	
	No. of patients at Risk	Event-free probability estimates (%) ^c	No. of patients at Risk	Event-free probability estimates (%) ^c	No. of patients at Risk	Event-free probability estimates (%) ^c
Time to Overall Response ^a						
Week 4	xxx	x.x	xxx	x.x	xxx	x.x
Week 10	xxx	x.x	xxx	x.x	xxx	x.x
Week 20	xxx	x.x	xxx	x.x	xxx	x.x
Week 30	xxx	x.x	xxx	x.x	xxx	x.x
Week 40	xxx	x.x	xxx	x.x	xxx	x.x
Week 50	xxx	x.x	xxx	x.x	xxx	x.x
Etc. (as appropriate)	xxx	x.x	xxx	x.x	xxx	x.x
Total number of events, n (%)	xx (xx.x)		xx (xx.x)		xx (xx.x)	
Total number of censored, n (%)	xx (xx.x)		xx (xx.x)		xx (xx.x)	
Percentiles (95%CI) (weeks) ^b						
25 th percentile	xx.x (xx.x, xx.x)		xx.x (xx.x, xx.x)		xx.x (xx.x, xx.x)	
Median	xx.x (xx.x, xx.x)		xx.x (xx.x, xx.x)		xx.x (xx.x, xx.x)	
75 th percentile	xx.x (xx.x, xx.x)		xx.x (xx.x, xx.x)		xx.x (xx.x, xx.x)	

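### Country-by-country closure can cut off progression-free patients before 24-week stable disease can be shown, yet CBR, and to a lesser extent ORR, counts them as failures

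*Protocol*

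**What the plan says.** **Closure.** A national study "will end when everolimus is locally reimbursed or commercialized for this indication" (Protocol 4.1; also 4.2 and 7.1.5); the other trigger is that no patient there remains on treatment. What follows is a 30-day safety follow-up and one update of progression status.

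**Enrolment.** "Enrollment will end in all participating countries by the time of registration/commercial availability of everolimus for the investigational indication", with 31 October 2014 as the outer limit (Protocol 4.1 and 5). The Rationale for Amendment 2 explains that limit: "as the investigational drug will be commercially available in the majority of the participating countries by the end of 2014". No section sets a minimum interval between the last enrolment and closure in a country.

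**Population and timing.** The full analysis set (FAS) is every treated patient (10.1). The main analysis is triggered by a median follow-up of 15 months, not a minimum (10.2).

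**Endpoints.** CBR takes a best response of CR, PR "or stable disease (SD), with duration of 24 weeks or longer, according to RECIST 1.1" (10.6.1.2). For ORR the protocol states: "To be assigned a best overall response of PR at least two determinations of PR or better at least 4 weeks apart before progression", with a matching rule for CR (10.6.1.1). Scans fall at Week 10 and every 10 weeks after that, each with a 2-week window, plus a mandated end-of-treatment (EOT) CT or MRI (Tables 7-1 and 7-2).

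**Handling.** Section 10.6.1 censors patients who leave without an event. Section 10.6.1.4 keeps patients of unknown response in the ORR denominator as non-responders. In SAP Table 8.1.1 the footnote on total N reads "It is the denominator for percentage (%) calculation", and a programmer's note says that the table is not a Kaplan-Meier analysis. The SAP lists "Patient is switched to commercial drug" as a reason for ending treatment (Table 1.3) and evaluation (Table 1.5.1). Neither rate has a rule for those patients.

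**The concern.** ORR and CBR are two of the three key secondary efficacy endpoints (Protocol Table 3-1), and both need time on study. Closure is administrative: it follows local launch, not the patient's disease. A patient who is progression-free when her country closes has not failed, but a simple proportion has no way to say so. Censoring, which protects PFS, does nothing for a Clopper-Pearson rate. The reported CBR would then mix drug effect with the gap between enrolment and launch. A reader comparing it with another study could not tell the two apart.

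**Working it through.** The plan has no sample-size or power figure to reproduce: N is up to 400, with no hypothesis test (10.7). The check is of scan dates and of the resulting proportion.

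**1. Time needed to qualify**

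- *24-week SD.* The Week 20 scan falls at 20 + 2 = Week 22 at the latest, which is under 24. The next scheduled scan is Week 30, at 30 − 2 = Week 28 at the earliest. The only other route is an EOT or unscheduled scan at Week 24 or later.
- *Confirmed response.* On scheduled scans, the second one can fall at 20 − 2 = Week 18. With the EOT scan as the second, it is (10 − 2) + 4 = Week 12.
- SAP Table 8.1.1 counts CR and PR of any duration towards CBR. Section 10.6.1.2 could be read as applying 24 weeks to responses too. I use the SAP reading, which gives the smaller loss.

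**2. Time guaranteed**

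None. If a country closes on the day its enrolment stops, the gap is zero. As an illustration only, enrolment on 31 October 2014 and closure on 31 December 2014 give 61/7 = 8.7 weeks. That is inside the Week 10 scan window, but too short for a confirmed response or for 24-week SD. With that closure date, anyone starting after 16 July 2014 has under 24 weeks, and anyone starting after 8 October has under 12.

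**3. How one patient is counted: stable, progression-free, closed out before Week 24**

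| Endpoint | Treatment in the plan |
|---|---|
| PFS (10.6.1.3) | Censored |
| CBR (SAP Table 8.1.1) | In N, without clinical benefit |
| ORR (10.6.1.4, SAP Table 8.1.1) | In N, non-responder; an earlier single PR stays unconfirmed |

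**4. Size**

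Let f be the share of the FAS with under 24 weeks from first dose to country closure, and p the true CBR, assumed equal in that group and the rest. Let r be the proportion of the cut-off group with a confirmed CR or PR by closure. Then

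reported CBR = p(1 − f) + r·f, so the loss is (p − r)·f, at most p·f.

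The documents give neither p nor f. Assuming p from 30% to 60%, with r = 0:

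| p | f = 5% | f = 10% |
|---|---|---|
| 30% | 28.5% | 27.0% |
| 50% | 47.5% | 45.0% |
| 60% | 57.0% | 54.0% |

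For p = 50%, f = 10% and N = 400, the planned table shows 180/400 = 45.0% (exact 95% CI 40.1 to 50.0). Leaving out the cut-off patients gives 180/360 = 50.0% (44.7 to 55.3).

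**The case against.** **What stands.**

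- Local availability also stops enrolment, so nothing supports assuming steady accrual up to October in the countries that close early. This reduces the number affected but creates no minimum gap.
- The EOT scan allows confirmation from about Week 12, and any confirmed CR or PR counts for CBR in the SAP. The loss therefore falls mainly on patients relying on stable disease, and ORR suffers less. If the SAP's wording on responses that need no confirmation were applied, ORR would suffer less still.
- Counting unknowns as non-responders is a stated, conservative choice for ORR, in a descriptive study. That supports keeping the FAS analysis primary.

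**What stands in part.** The SAP already shows pieces of the problem: columns for patients enrolled from 1 July 2014 (Table 1.1), counts of switched patients (Tables 1.3 and 1.5.1), time from last scan to study end in censored patients (Table 8.2.1), and Kaplan-Meier estimates at Weeks 20 and 30 (Table 8.3.1). None of these adjusts either rate. The sensitivity table, 8.3.3, is for PFS. The SAP supplied is mostly table shells, so a rule may sit in text not seen here.

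**Stronger readings that a reader might infer.**

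- *A very large bias.* Accrual of (198 − 114)/224 = 0.375 per day for 123 more days adds 46 patients, N about 244. If every country closed on 31 December 2014, 46 × 107/123 = 40 of 244 (16%) would have under 24 weeks. At N = 400 it would be 202 × 107/123 = 176 (44%). A true CBR of 50% would show as about 42% or 28%. The documents do not support this. They give no closure dates and expect availability in only a majority of countries by then. It also conflicts with the 15-month trigger. At N = 244, patient 122 enrols about 8/0.375 = 21 days after 18 November 2013, so median follow-up at closure is about 12.7 months. At N = 400, over half enrol after 30 June 2014, so it is at most about 6 months.
- *A biased Asian/Non-Asian comparison.* Both closure and region are defined by country, so a difference is possible. Without launch dates it is not shown.

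**Conclusion.** The concern holds. On the current text, a progression-free patient whose country closes early is censored for PFS but counted without clinical benefit, and nothing in the documents corrects this. The bias can only be downward. It affects CBR most and ORR less.

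Its size cannot be fixed from the documents, because it depends on country closure dates. The usable bound is a loss of at most true CBR × f, for example 5 points at f = 10% and a true CBR of 50%. It assumes that cut-off patients would have had the same CBR as the others, and it shrinks where they already have a confirmed response. This calls for a supportive analysis, not a change to the primary one.

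**What to change.** Keep the FAS analysis as primary. In Protocol 10.6.1.1 and 10.6.1.2 and SAP Table 8.1.1 (with its subgroup copies S1 to S4.8.1.1):

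1. Add a supportive ORR and CBR in FAS patients whose first dose came early enough before their country's closure date to reach the scan that can show 24-week SD. Prespecify one cut-off, for example 30 + 2 = 32 weeks. The set is defined by calendar dates alone, so it does not depend on outcome.
2. Add a Week 24 row to the Kaplan-Meier PFS table (8.3.1). It uses the censored patients and is a companion to CBR, not a substitute.
3. Report how many patients were switched to commercial drug or closed out before Week 24 without progression, as a separate count outside SD and Unknown.
4. State the denominator once. The footnote divides by total N, while the programmer's note defines n as patients with non-missing data.

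**Cost.** SAP wording, one repeated table, one row and one count, using first-dose dates already collected and closure dates that the sponsor sets. The supportive set is smaller, so its interval is wider. In the extreme case of every country closing on 31 December 2014, the 32-week cut-off falls on 21 May 2014. It would remove about 40 × 0.375 + 46 = 61 of 244 patients (25%), or 15 + 202 = 217 of 400 (54%). With fewer early closures the loss is less.
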